### Missing dates and times

#### *Adverse event data and non-fatal outcome events*

Missing or incomplete AE dates are imputed according to BI standards (see DM&SM “Handling of missing and incomplete AE dates”).[\(1\)](#)

In the unlikely case that only the year is documented, the day and month will be imputed as 01 Jan unless the subsequently derived date is before randomisation; in this case the date of randomisation will be used as start date. If year and month is present the day will be imputed as first of the month unless the subsequently derived date is before randomisation; in this case the date of randomisation will be used.

#### *Missing information on the date of first administration of trial drug*

If a patient was randomised, but the date of first drug administration is missing, the date of the first drug administration will be set to the date of randomisation. If the date of first administration is partially missing with the month and year present, the day will be set to the date of randomisation, if randomisation was in the same month. If randomisation was in the month prior to the first drug administration the missing day will be imputed as the first day of the month.

#### *Missing information on the time of administration of trial drug*

A missing time of first drug administration will be imputed as 12:00 o'clock noon. Missing administration times at on-treatment visits will be imputed by 8:00 o'clock in the morning.

*Missing information on the date of last administration of trial drug*

If this date is missing, it will be imputed by the date of the respective visit.

If the date is incomplete with only month and year and the respective visit date is missing, the date of last drug administration will be imputed by the last day of this month. If this would be later than the date of trial completion, then the date of trial completion will be used for imputation.

If a patient is lost-to-follow up, no date of last drug administration is reported and the date of the respective visit is not available, the date of last drug administration is set as the date of trial completion.

For a patient who dies in the treatment phase with no information on the date of last drug administration, the date is set as the date of death, assuming that the patient took the medication until the date of death.

Rules following this are described in [Section 6.1.1](#).

If after imputation, the date of trial completion is before the date of last drug administration, the start of the post-study period is defined as the maximum of trial completion +1 day, the date of the last visit +1 day and the start of the post-treatment period+1 day.

*Missing information on other dates of administration of trial drug (excluding first and last administration)*

A missing date will be imputed by the respective visit date.

If month and year are available and equal to the visit date, the date is imputed by the day of the respective visit. If the documented month is later than the month of the visit date, the day will be imputed by the 1st of the month.

*Missing information on date of randomisation*

If the date of randomisation differs between IXRS and eCRF, the randomisation date as in IXRS will be used. If the date of randomisation is missing in the eCRF, it will be imputed by the date obtained from IXRS.

*Missing information on the birth date*

If only the year of birth is known, the day and month of birth will be imputed as 01 January.

*Missing information on concomitant therapy dates*

For incomplete date information the midpoint of the possible interval will be used. That means, if only the year is present the day and month will be imputed as 01 July, if year and month is present the day will be imputed as 15.

If the year is missing, the date will be considered missing.

If this leads to contradictions for the start or end date of a concomitant therapy (e.g. imputed end date before documented start date) a partial end date will be imputed as the end of the interval or a partial start date will be imputed as the start of the interval in the database to resolve this contradiction.

*Missing date of trial completion (=last contact or date of death)*

If the date is completely missing the following rules will be applied:

If a patient did not die (no corresponding vital status and/or adverse event information), the date of trial completion will be imputed by the last date the patient was known to be alive.

If a patient died and has not withdrawn consent, this date will be imputed by the date of death.

If a patient has withdrawn informed consent, this date will be imputed by the date of IC withdrawal.

If the date is incomplete with only month and year reported, the date will be imputed by the first day of this month.

Exception:

If the date last known to be alive, or respectively date of IC withdrawal is after the imputed date, the date of trial completion is to be imputed by this date.

If a patient died and has not withdrawn consent and the date of death is known, the date of trial completion will be imputed by the date of death.

Missing onset time of hypoglycaemia/ missing plasma concentration

If onset times are available for hypoglycaemic events then those events are only considered as on-treatment, if the onset is at or after the time of first drug administration. Missing onset times on the day of first drug administration will be imputed as the time of the start of drug administration and those hypoglycaemias will be counted as on treatment. Missing onset times on other days will be imputed as 0:00.

If a patient has multiple hypoglycaemic episodes and some of them have missing plasma glucose values, those with missing values will be excluded from the derivation of the minimum glucose level (worst episode).

Laboratory data

Missing safety laboratory data will not be replaced.

Laboratory data outside the limits of quantification

Biomarker measurements of HbA1c, fasting plasma glucose, pro-insulin and c-peptide below the limit of quantification will be imputed by 2/3 times the lower limit of quantification for analysis. Values above the upper limit of quantification will be replaced by 1.5 times the upper limit of quantification.

## **6.7 BASELINE, TIME WINDOWS AND CALCULATED VISITS**

The actual number of visits that a patient attends depends on when the patient gave informed consent (randomisation period: Dec, 2010 to Dec, 2012).

### **6.7.1 Baseline**

With regard to efficacy and safety endpoints, the term "baseline" refers to the last observed/available measurement prior to administration of any randomised study medication.

A missing baseline value at the randomisation (Visit 2) may be replaced by a value at the beginning of the placebo run-in period (Visit 1b).

The following rule applies to baseline laboratory and ECG measurements, if visit and date/time of lab/ECG sample is not in a corresponding sequence (i.e. earlier date/time documented for a later visit):

If such a discrepancy occurs before first study medication intake, then the observations are sorted by date, time and visit and the last observation up to and including the time of the first administration of study drug is selected as baseline value for analyses.

The following considerations apply for laboratory measurements, if the time of the sample is missing on the day of first study medication intake:

- a) For HbA1c, FPG, triglycerides, proinsulin, C-peptide and antibodies: the measurement will not be considered as baseline
- b) For total cholesterol, HDL cholesterol, LDL cholesterol, creatinine, eGFR, urinary albumin, UACR and all safety lab investigations:  
The last measurement on this day will still be considered as baseline measurement.

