Lipid profile			X			X			X			X		X	
Adverse events	X	X	X	X	X	X	X	X	X	X	X	X	X	X	X
Concomitant Therapy	X	X	X	X	X	X	X	X	X	X	X	X	X	X	X
Dispense double-blind medication	X	X	X	X	X	X	X	X	X	X	X	X	X	X	
Medication compliance check	X	X	X	X	X	X	X	X	X	X	X	X	X	X	X

Proprietary confidential information.

© 2019 Boehringer Ingelheim International GmbH or one or more of its affiliated companies. All rights reserved.

This document may not - in full or in part - be passed on, reproduced, published or otherwise used without prior written permission.

- A Visit 1b to be performed within 1 week from Visit 1a
- B Overnight fasting (10 hours no food and only water)
- C HbA1c measured at Visit 1a will be used for inclusion
- F For female patients (local urine pregnancy test in women of child bearing potential). More frequent testing can be done if required by local regulations/authorities.
- G Home blood glucose monitoring (HBGM) device provided at Visit 1b. The patient should be instructed to bring their HBGM device to the clinic at least at the specified visits for an additional measurement of fasted glucose.
- H Visit 1a safety laboratory only includes ALT (SGPT), AST (SGOT), alkaline phosphatase, serum creatinine, urine analysis and urine albumin and creatinine, in addition to HbA1c and does not need to be collected in fasted state.
- I Body Mass Index will be calculated automatically.
- J Maximal time window between two visits during titration phase is 5 weeks and during maintenance phase 18 weeks.
- K Calculated based on MDRD formula (see Section [5.2.3.4](#)). This formula considers the race as an adjustment factor, therefore, the race must be known (and will be collected) for accurate estimation.
- M Clinically relevant abnormalities found at physical examination, vital signs or ECG that are not pre-existing prior to signing of informed consent (study inclusion) should be reported as adverse event. If such abnormalities already pre-exist prior study inclusion they should be considered as baseline conditions.

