Administration of the study medication is once daily. Patients should be instructed to take their trial medication once daily with 150 mL of water.

To ensure a dose interval of about 24 hours, the medication should be taken at the same time every day. If a dose is missed by more than 12 hours, that dose should be skipped and the next dose should be taken as scheduled. No double doses should be taken. Study medication should be taken shortly before or during a meal.

In some situations, it might be necessary to interrupt study medication temporarily. Patients are encouraged to re-start study treatment after an interruption if appropriate

Proprietary confidential information.

© 2019 Boehringer Ingelheim International GmbH or one or more of its affiliated companies. All rights reserved.

This document may not - in full or in part - be passed on, reproduced, published or otherwise used without prior written permission.

in the opinion of the investigator and if not contraindicated. In case the patient is re-instituted on study treatment, the preferred dosage for glimepiride/glimepiride placebo is the dose used before stopping treatment (unless hypoglycaemia was the reason to temporarily stop treatment). In case there is a need for further adjustments after this re-institution the guidance for treatment initiation should be followed.

Patients should be instructed not to take their trial medication in the morning of visit days as they will be dosed whilst in the clinic. Patients who fail to do so should have the visit rescheduled as soon as possible, ideally on the following day. Background and/or rescue medication will be taken as prescribed including visit days.

Patient visits should be routinely scheduled in the morning (preferably between 7:00 AM and 11:00 AM), at approximately the same time at each visit. The actual date/time of trial drug administration at the study visit will be recorded in the eCRF.

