#### 5.1.2 Assessment of efficacy

*HbA1c*:

Blood samples for the determination of  $HbA_{1c}$  will be taken according to the [Flow Chart](#). The blood sample can be taken at any time during the visit. The samples will be analysed at a central laboratory or its affiliates having a National Glycohemoglobin

Proprietary confidential information.

© 2019 Boehringer Ingelheim International GmbH or one or more of its affiliated companies. All rights reserved.

This document may not - in full or in part - be passed on, reproduced, published or otherwise used without prior written permission.

Standardization Program (NGSP) Level I certificate. Further details about sample handling, shipment, and assay procedures can be found in the Investigator's Site File (Lab manual).

*FPG:*

Blood samples for the determination of FPG will be taken according to the [Flow Chart](#) after an overnight fast (10 hours no food and only water). At all respective visits, the samples should be taken before breakfast and before trial drug administration. The samples will be measured at a central laboratory using validated assays. Further details about sample handling and shipment can be found in the Investigator Site File (Lab manual).

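### A day-1 HbA1c without a clock time is refused as baseline, although the protocol does not require HbA1c before the dose and the only named replacement visit has no HbA1c

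*SAP*

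**What the plan says.** SAP 6.7.1 defines baseline as the value that "refers to the last observed/available measurement prior to administration of any randomised study medication". It adds that a missing Visit 2 value "may be replaced by a value at the beginning of the placebo run-in period (Visit 1b"). No other replacement visit is named.

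The section then covers samples with no clock time on the day of first study drug:

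- List a): "For HbA1c, FPG, triglycerides, proinsulin, C-peptide and antibodies: the measurement will not be considered as baseline".
- List b), covering total, HDL and LDL cholesterol, creatinine, eGFR, urinary albumin, UACR and all safety laboratory tests: "The last measurement on this day will still be considered as baseline measurement".

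No reason is given for the split.

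Protocol 5.1.2 treats HbA1c and FPG differently. For HbA1c, "The blood sample can be taken at any time during the visit". For FPG, "the samples should be taken before breakfast and before trial drug administration". Protocol 4.1.4 tells patients not to take trial medication on the morning of a visit, "as they will be dosed whilst in the clinic". Footnote C of the protocol flow chart says that the HbA1c "measured at Visit 1a will be used for inclusion".

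**The concern.** List a) guards against a sample taken after the first dose being used as a pre-dose value. That guard matters only where the order of sample and dose matters. For HbA1c the protocol does not ask for a particular order, so the SAP discards a value because it lacks information that the protocol did not treat as relevant.

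What happens next is not clearly specified. The replacement sentence points to a visit with no HbA1c. The general definition points to Visit 1a. A programmer could follow either one. The first leaves the patient without a baseline. The second supplies an older value on which the patient was selected. Either is worse than the Visit 2 value already in the database.

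Baseline HbA1c is the covariate in the HbA1c ANCOVA and MMRM (SAP 7.5.2.2.1) and appears in the baseline tables (SAP 7.1).

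**Working it through.** The plan states no figure to reproduce, so this is a check of the rules and the visit schedule against each other.

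**1. Does the order of sample and dose matter for HbA1c in these documents?**

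| Source | HbA1c | FPG |
|---|---|---|
| Protocol 5.1.2, sampling relative to dose | any time in the visit | before dosing |
| SAP Table 6.7.2: 1, days after drug stop still counted as on-treatment | 7 | 1 |
| SAP 6.7.1, untimed day-1 sample | refused | refused |

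The first two rows separate the slow marker from the fast one. The third treats them alike. SAP 6.6 is also more tolerant of the opposite gap: a missing time of first dose is set to noon. Visits are preferably held between 7 and 11 in the morning, so timed morning samples then count as pre-dose.

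**2. Which pre-treatment values exist?** From the flow chart columns:

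| Parameter | Visit 1a (day -35 to -15) | Visit 1b (day -28 to -14) | Visit 2 (day 0) |
|---|---|---|---|
| HbA1c | yes | no | yes |
| FPG | no | yes | yes |
| Lipid profile | no | no | yes |

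The Visit 1b replacement works for FPG. It cannot work for HbA1c.

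**3. Is the refused sample used elsewhere?** SAP 6.7.3 counts days as date of measurement - treatment start date + 1. For a sample on the day of first dose this is 0 + 1 = 1. The first on-treatment HbA1c window (Visit 6, SAP Table 6.7.3: 2) opens on day 2. The value is therefore neither baseline nor on-treatment in the by-visit analyses.

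**4. What replaces it?**

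- *General definition applied:* the Visit 1a value, 15 to 35 days before randomisation and before the placebo run-in. Entry required it to lie in 6.5-8.5% or 6.5-7.5%, depending on background therapy (Protocol 3.3.2), and a value was not retested merely because it missed those limits (Protocol 3.3). A value selected in this way is open to regression to the mean.
- *Only the Visit 1b sentence applied:* no baseline. SAP 7.5.2.2.1 includes in the analysis over time only patients with a baseline and at least one on-treatment value, so the patient drops out.

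**5. How many patients?** Neither document gives a rate of missing sample times. With about 6000 randomised patients, each 1% of untimed Visit 2 samples is 0.01 x 6000 = 60 patients; an assumed 3% would be 0.03 x 6000 = 180. The rate may be close to zero, because Protocol 5.2.3.3 asks for the exact date and time of blood sampling on the requisition form.

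**6. Which analyses are reached?** The primary and first key secondary endpoints are Cox models with a treatment term only (SAP 7.4.1.1, 7.5.1). The second and third key secondary endpoints use HbA1c at or below 7.0% at Final Visit (SAP 5.2.1), not change from baseline. One indirect route exists on paper. SAP 6.6 carries baseline HbA1c forward for a patient rescued before any on-treatment HbA1c, and fills a missing final HbA1c by the same method. An untimed sample, early rescue and a missing final value would all have to occur in one patient, so I treat this route as negligible. What remains is the HbA1c change-from-baseline analyses, which SAP 7.5.2 calls exploratory, and the baseline tables.

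**The case against.** The best defence is that list a) applies the SAP's own definition literally. Baseline must precede the first dose, and SAP 6.7.2 uses the clock time of first dose to separate pre-treatment from on-treatment values. Because HbA1c may be drawn at any time in a visit with in-clinic dosing, an untimed sample may really be post-dose. List b) is the relaxation, and where it stops is a conservative choice. This stands as far as it goes: the rule is coherent. It does not explain why HbA1c is treated more strictly than creatinine or cholesterol when the protocol sets no pre-dose condition for it.

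Four stronger readings are tempting and are not supported:

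- *The baseline is necessarily lost.* It is not. The Visit 1a HbA1c decides eligibility, so every randomised patient should have one, and it meets the general definition. Background therapy had to be stable, and SU or glinide was stopped only at Visit 2, so it is a reasonable pre-treatment value. The gap is that the SAP does not say it is the fallback.
- *A same-day dose cannot change HbA1c or antibodies.* Neither document says so. For HbA1c the sampling rule gives indirect support; for antibodies there is none.
- *Antibody results are lost.* SAP 6.6 and 7.5.2.2.2 show that antibodies are only described at baseline, without replacement of missing values. Their sampling times do not appear in the public flow chart, so whether an earlier sample exists cannot be checked.
- *The treatment comparison is biased.* The rule works alike in both arms and the models adjust for baseline. No bias in the difference is shown.

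It is also fair to note that triglycerides, in the same list, have no earlier scheduled value either. Lack of a replacement is therefore not by itself the argument. The argument is that the protocol does not ask for HbA1c before the dose.

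**Conclusion.** The point holds in a limited form. An untimed day-1 HbA1c is refused as baseline for a reason that the protocol does not support, and the replacement sentence names a visit without HbA1c. The outcome is either an older value used for selection or, on the narrower reading, exclusion from the analysis over time.

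The size is small and cannot be calculated, because no rate of missing times is given; the 60 patients per 1% is only a scale. The effect is confined to exploratory HbA1c analyses and baseline tables. This is a free improvement, not an error that threatens a conclusion. It rests on one inference: the absence of a pre-dose requirement in Protocol 5.1.2 means that the order of sample and dose was not considered important for HbA1c.

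**What to change.** In SAP 6.7.1:

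1. Move HbA1c from list a) to list b), so that the last value on the day of first dose serves as baseline when its time is missing.
2. Add one sentence stating that, if no Visit 2 HbA1c exists, the Visit 1a value is the baseline, since Visit 1b has none.
3. Optionally move antibodies as well, with a one-line reason, after checking their sampling schedule in the full protocol.

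The cost is one parameter name moved and one sentence added before unblinding. No new data are needed and no other rule changes. The price is that an occasional HbA1c drawn shortly after the first dose will count as baseline, as list b) already allows for its own parameters.

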### **6.7.2 Time windows for assignment to on-treatment phase**

Measurements taken prior to the first intake of randomised study drug will be considered pre-treatment values.

The date and clock time of the first drug administration will be used to separate pre-treatment from on-treatment values. Measurements taken after the first intake of randomised study drug will be considered on-treatment values if they have been obtained up to the end of the parameter-specific follow-up period as defined in [Table 6.7.2: 1](#): they will be assigned to the randomised study drug for analyses.

Measurements taken after the end of the follow-up period will be considered post-treatment values.

Table 6.7.2: 1 Endpoint specific follow-up time for assignment to active treatment

Endpoint	Last day of assignment to treatment (days after study drug stop date)
HbA1c	7
FPG	1
Body weight	7
Adverse events	7
Asymptomatic hypoglycaemia, that is not considered as adverse events	7
Laboratory measurements including eGFR and UACR	7
Vital signs	7
Waist circumference	7

### 6.7.3 Time windows for assignment to visits in the on-treatment phase

Analyses by study visit are performed to assess the effects of treatment over time. Planned measurements are not always taken on the exact day or time as planned in the protocol. To be able to use measurements in analyses over time, time windows are defined to also assign measurements deviating from the planned schedule to a study visit. Measurements deviating from the planned visit schedule will be allocated to the planned visit on the basis of the actual number of days on treatment (defined as (date of measurement – treatment start date + 1)).

Pre-treatment values will be assigned to a visit according to the nominal visit number as recorded on the eCRF or as provided by e.g. the laboratory.

On-treatment measurements of HbA1c, FPG, weight, Total cholesterol, LDL cholesterol, HDL cholesterol, Triglycerides, Creatinine, eGFR, urinary albumin, UACR, vital signs and waist circumference will be assigned to visits based on time windows around the planned visit dates.

These time windows are defined based on the planned number of days after the date of first administration of study drug (Visit 2).

The midpoint between two on-treatment visits defines the end of a time window, with the midpoint being included in the time window of the preceding visit. The end of the time window of the last on-treatment visit (end of treatment (EOT)) is endpoint dependent.

Reasons to base the time windows on the actual treatment start date rather than the randomisation date are:

- If first intake of study drug shows a large delay by e.g. more than one week after the date of randomisation, a measurement taken four weeks after randomisation rather reflects the

drug effect after three weeks than after four weeks and thus may underestimate the treatment effect at this visit.

- With large delays of the introduction of study drug after the randomisation, the time window for the first on-treatment visit could include times the patient was not yet on study drug.

The time window for the first visit after randomisation starts on the day after the first intake of study drug. This maximises the number of measurements used in by visit analyses and provides consistency with the planned last observation carried forward (LOCF) approach (as well as the approach to include patients with a baseline and at least one on-treatment measurement into the analysis).

[Table 6.7.3: 1](#) shows the time windows for FPG, planned to be measured at every visit.

Table 6.7.3: 1 Time windows for visits for FPG

Visit number	Planned days after randomisation	Planned days on treatment	Time window start* based on planned days on treatment	Time window end* based on planned days on treatment
2	0	1	NA	1**
3	28	29	2	43
4	56	57	44	71
5	84	85	72	99
6	112	113	100	169
7	224	225	170	281
8	336	337	282	393
9	448	449	394	505
10	560	561	506	617
11	672	673	618	729
12	784	785	730	841
13	896	897	842	953
14	1008	1009	954	1065
15	1120	1121	1066	1177
16	1232	1233	1178	1289
17	1344	1343	1290	1401
18	1456	1457	1402	1513
19	1568	1569	1514	1625
20	1680	1681	1626	1737
21	1792	1793	1738	1849
22	1904	1905	1850	1961
23	2016	2017	1962	2073
24	2128	2129	2074	2185
25	2240	2241	2186	2297
26	2352	2353	2298	2409
27	2464	2465	2410	2521
28	2576	2577	2522	2633
29	2688	2689	2634	2745
30	2800	2801	2746	Study drug stop date + x days***

\*actual days on treatment

\*\*has to be pre-treatment value

\*\*\*The definition of x is endpoint specific, cf. [Table 6.7.2: 1](#).

As e.g. HbA1c and weight are not measured at every visit, the time windows until visit 6 would be as shown in [Table 6.7.3: 2](#) (from visit 7 on windows as described above apply):

Table 6.7.3: 2 Time windows until visit 6 for e.g. HbA1c and weight

Visit number	Planned days after randomisation	Planned days on treatment	Time window start* based on planned days on treatment	Time window end* based on planned days on treatment
2	0	1	NA	1**
6	112	113	2	170

\*actual days on treatment

\*\*has to be pre-treatment value

For further visits beyond visit 30 the same concept is applied.

Only one observation per time window will be selected for analysis at a visit – the value will be selected which is closest to the protocol planned visit day. If there are two observations which have the same difference in days to the planned day or if there are two observations on the same day, the first value will be used. If there are multiple values within the time window of the last visit, including a value on the last day of drug intake, the value on the last day of drug intake is used as the value of the last visit.

For LOCF imputation (including interpolation), the last observed on-treatment value will be carried forward, whether or not it was selected in the previous time window (see [Section 6.6](#)).

The assignment of all measurements, including on-treatment and off-treatment measurements, to visits will be performed accordingly.

For all variables any measurement obtained in the window of +8 days to + 44 days after last study drug intake will be assigned as “Follow-up measurement”, corresponding to planned measurement at 30 days after last study drug stop.

